#### **4.5.2.1. Adverse Events of Special Interest**

The following will be considered adverse events of special interest (AESI) for the purpose of analyses.

- Cardiovascular (CV) adverse events (AEs)
- Gastrointestinal (GI) adverse events (AEs)
- *Clostridioides difficile*-associated diarrhea (C. difficile AEs)
- Acetylcholinesterase Inhibition (AChE-I)

The AESIs Cardiovascular (CV) and Acetylcholinesterase Inhibition (AChE-I) will be identified using project-level Terms of Interest (ToI) lists obtained from the GSK coding specialist in consultation with the study safety expert.

Details of the planned displays for AESIs are provided in Output programming specifications (OPS) and will be based on GSK Data Standards and statistical principles.

#### **4.5.2.1.1. Cardiovascular (CV) and Gastrointestinal (GI) AESIs**

Gastrointestinal (GI) AESIs are defined as AEs within a gastrointestinal SOC.

Cardiovascular AESIs are defined as AEs with PTs that match the terms listed in the ToI list. The counts and percentages of participants with an event will be summarized and listed by PT, and the maximum grade for CV and GI AESIs. The most current version of MedDRA will be used as applicable at the time of this study SAC.

#### **4.5.2.1.2. *Clostridioides difficile*-associated diarrhea (*C. difficile* AEs) AESIs**

*Clostridioides difficile*-associated diarrhea (*C. difficile*) AESIs (PTs *Clostridium difficile* infection and *Clostridium difficile* colitis) will be included in the overview of summary of adverse events (AEs). *C. difficile* laboratory testing results are collected and recorded on distinct eCRF pages, which will be presented in a participant listing.

#### **4.5.2.1.3. Acetylcholinesterase Inhibition (AChE-I) AESIs**

Any reported AE listed in AChE-I TOI listing with a start time no later than 12 hours after the last dose administered, as evaluated by the investigator as per the [DAIDS, 2017] grading criteria provided in protocol Section 10.10 and Appendix 10: Division of AIDS table for grading the severity of adult and pediatric AEs, version 2.1, July 2017, will be included in the programmatic identification of AChE-I related AESI. The most current version of MedDRA will be used as applicable at the time of this study SAC.

Cumulative grade score of Acetylcholinesterase-Inhibition (AChE-I) will be calculated as the sum of the grade of each reported AE. This enables the number of AEs and the severity of each AE to be considered. The grading scale is defined as

Cumulative Grade:	0	1	2	3	4
Cumulative Grade Score:	0	1 to 3	4 to 6	7 to 10	≥11

For instance, if a participant reports two AEs, one of Grade 1 and the other of Grade 3 their cumulative grade score of 4 would result in cumulative grade 2. This will be calculated for all AChE-I events, non-GI AChE-I events and GI AChE-I events. This will be calculated for All AChE-I events, non-GI AChE-I events and GI AChE-I events which will be summarized.

Acetylcholinesterase inhibition AESIs will be listed and tabulated by system organ class (SOC) and preferred term (PT) and maximum grade. Non-GI AChE-I events will also be

summarized. A separate table will summarize the AChE-I AESI by the number of events and unique preferred terms. In addition, time of onset (time from first dose to the onset of first event in hours), duration, and lag time (the time from last dose to the end date/time of the last event for subjects whose end date/time of the last event is after treatment end date/time) of AChE-I events will also be summarized, and repeated for non-GI AChE-I and GI AChE-I events.

AChE-I events with a start time less than 6 hours after the latest dose administered will also be flagged in listings.

Additionally, Adverse Events of Torsade de Pointes/QT Prolongation SMQ by PT will also be summarized based on the SMQs listed in the OPS. The most current version of MedDRA will be used as applicable at the time of this study SAC.

#### **4.5.2.2. COVID-19 Assessment and COVID-19 AEs**

Not Applicable.

#### **4.5.2.3. Impact of COVID-19 Pandemic on Safety Results**

This study is conducted in the post-pandemic phase and therefore not applicable.

#### **4.5.3. Classification and analysis of safety signals**

As per GSK Guidance document (VQD-REF-019518 Statistical considerations for Assessment of Adverse Reaction for GDS and VDQ-REF-019393 Developing and Updating the Adverse Reaction of the Global datasheet) “Adverse reactions” (ARs) are undesirable effects, reasonably associated with use of a product that may occur as part of the pharmacological action of the product or may be unpredictable in its occurrence.”

CCI

[REDACTED]. Qualitative evaluation of the potential ARs will be used to determine if there is sufficient evidence of a causal association with the investigational product.

##### **4.5.3.1. Multiplicity Adjustment**

As screening for potential ARs is intended as an aid to medical judgment rather than to be used for decision making, no adjustment for multiplicity will be applied.

#### **4.5.3.2. Qualitative Causality Assessment**

Qualitative evaluation of the potential ARs will be performed to determine if there is sufficient evidence of causal association with gepotidacin. The following data displays will be produced for each AE of potential ARs to support the qualitative causality assessments.

CCI

Additional data displays may be generated as needed to assist with further qualitative assessment of the potential ARs once the safety data is reviewed. The generated data displays may be useful in evaluating the likelihood of a causal association and the strength of causality by assessing the consistency according to clinically relevant attributes.

#### **4.5.4. Additional Safety Assessments**

##### **4.5.4.1. Laboratory Data**

Laboratory evaluations including the analyses of chemistry laboratory tests, hematology laboratory tests, urinalysis, and liver function tests (as listed in Protocol Appendix 7) will be based on GSK Core Data Standards. Laboratory data will be graded by a Central Laboratory.

Descriptive statistics (n, mean, standard deviation (SD), median, minimum value (min), and maximum value (max)) will be presented for quantitative measurements of key continuous laboratory parameters at baseline and worst-case post-baseline assessments from unscheduled visits (only if there are at least 5 participants with data at unscheduled visits). Participants listing for all laboratory parameters will be produced.

Abnormal liver chemistry results will be summarized by increasing folds above the upper limit of normal (ULN) including tests of interest and thresholds as follows:

- ALT or AST  $> 3 \times \text{ULN}$  and Total Bilirubin  $> 2 \times \text{ULN}$
- ALT or AST  $> 3 \times \text{ULN}$  and ALP  $< 2 \times \text{ULN}$  and Total Bilirubin  $\geq 2 \times \text{ULN}$
- ALT or AST  $> 3 \times \text{ULN}$  and Total Bilirubin  $> 1.5 \times \text{ULN}$
- $(\text{ALT}/\text{ALT ULN})/(\text{ALP}/\text{ALP ULN}) > 5$  and ALT  $> 3 \times \text{ULN}$  \*
- ALT or AST  $\geq 20 \times \text{ULN}$
- ALT or AST  $\geq 10 \times \text{ULN}$
- ALT or AST  $\geq 8 \times \text{ULN}$
- ALT or AST  $\geq 5 \times \text{ULN}$
- ALT or AST  $\geq 3 \times \text{ULN}$
- ALT  $\geq 20 \times \text{ULN}$
- ALT  $\geq 10 \times \text{ULN}$
- ALT  $\geq 8 \times \text{ULN}$
- ALT  $\geq 5 \times \text{ULN}$
- ALT  $\geq 3 \times \text{ULN}$
- AST  $\geq 20 \times \text{ULN}$
- AST  $\geq 10 \times \text{ULN}$
- AST  $\geq 8 \times \text{ULN}$
- AST  $\geq 5 \times \text{ULN}$
- AST  $\geq 3 \times \text{ULN}$
- Total Bilirubin  $> 2 \times \text{ULN}$
- Total Bilirubin  $> 1.5 \times \text{ULN}$

\*: sign of hepatocellular injury, ALT and ALP values must occur on the same day.

The severity of renal impairment will be evaluated using estimated by creatinine clearance (CCr) using the Cockcroft and Gault formula (1973):

$$\text{creatinine clearance (mL/min)} = (((140 - \text{age in year}) \times (\text{weight in kg})) \times 0.85) / 72 \times (\text{Serum creatinine in mg/dL})$$

Severity of renal impairment will be categorized based on creatinine clearance as below (rounded to the nearest integer):

- Normal ( $\geq 90 \text{ mL/min}$ )
- Mild ( $\geq 60 \text{ to } 89 \text{ mL/min}$ )

- Moderate ( $\geq 30$  to 59 mL/min)
- Severe ( $< 30$  mL/min)

Details of the planned displays for clinical laboratory evaluations are provided in Output programming specifications (OPS) and will be based on GSK Data Standards and statistical principles.

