### 6.1.2 Demographic and Baseline Characteristics

Demographic characteristics such as age, sex, race, ethnicity, childbearing potential, baseline renal impairment category, height, weight, and body mass index (BMI), and baseline history of acute cystitis recurrence will be summarized and tabulated for study treatment using participants in ITT and primary clinically evaluable at 24 hours ( $\pm 4$  hours) analysis set.

Descriptive statistics will be presented for age, height, weight, and BMI. Counts and percentages will be presented for age category ( $\leq 50$  and  $> 50$ ), sex, race, ethnicity, childbearing potential.

Individual participant demographics characteristics will be presented in listings.

CCI

A large black rectangular box redacting content.

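### The Cockcroft and Gault formula in SAP 4.5.4.1 lacks brackets around its denominator; if coded as printed, the descriptive baseline renal impairment category would be wrong

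*SAP*

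**What the plan says.** SAP 4.5.4.1 (Laboratory Data) sets the method: "The severity of renal impairment will be evaluated using estimated by creatinine clearance (CCr) using the Cockcroft and Gault formula (1973". It then prints an equation on one line. In symbols, with age in years, weight in kg and Scr for the last term ("Serum creatinine in mg/dL"), it reads (((140 − age) × weight) × 0.85) / 72 × (Scr). The brackets balance, and none encloses 72 together with Scr.

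The result feeds four classes: "Severity of renal impairment will be categorized based on creatinine clearance as below (rounded to the nearest integer"). The classes are Normal (90 mL/min or more), Mild (60 to 89), Moderate (30 to 59) and Severe (below 30).

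SAP 6.1.2 lists the "baseline renal impairment category" among the characteristics to be tabulated for the ITT and CE24 sets.

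**The concern.** Under the usual order of operations, a slash followed by a multiplication sign divides by 72 and then multiplies by creatinine. Clearance then increases with creatinine.

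The documents themselves show that this direction is wrong. The SAP scale makes low clearance the severe class. Protocol 5.2, exclusion 13, names clearance below 30 mL/min and clinically significant elevated creatinine as alternative signs of significant renal impairment. With the printed formula, raised creatinine would move a participant towards Normal.

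At stake is the description of the enrolled population's renal function. Protocol 2.3.1 reports a substantial rise in Cmax and AUC in severe renal impairment, so readers of the safety results may look at this table.

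**Working it through.** **Inputs from the SAP.** The constants 140, 0.85 and 72, rounding to the nearest integer, and the cut-offs 90, 60 and 30 mL/min (4.5.4.1).

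**Inputs assumed.** Age, weight and creatinine. The documents give no worked example and no creatinine distribution, so there is no figure of the plan's own to reproduce.

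**Formulas.** Let K = (140 − age) × weight × 0.85 / 72.
- As printed: K × Scr.
- With the denominator bracketed: K / Scr.
- Ratio, printed to bracketed: (K × Scr) / (K / Scr) = Scr². The ratio is 1 only at 1.0 mg/dL. Age and weight enter both readings identically through K.

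**Example: 40 years, 70 kg.** (140 − 40) × 70 × 0.85 = 5950, and K = 5950 / 72 = 82.6.

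| Scr (mg/dL) | As printed | Bracketed |
|---|---|---|
| 0.7 | 82.6 × 0.7 = 57.8 → 58, Moderate | 5950 / 50.4 = 118.1 → 118, Normal |
| 1.0 | 82.6 → 83, Mild | 82.6 → 83, Mild |
| 2.0 | 82.6 × 2.0 = 165.3 → 165, Normal | 5950 / 144 = 41.3 → 41, Moderate |

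**Range over other assumed profiles.**
- 30 years, 65 kg: at 0.5 mg/dL, 42.2 (Moderate) as printed against 168.8 (Normal); at 0.9, 76.0 (Mild) against 93.8 (Normal); at 1.5, 126.6 (Normal) against 56.3 (Moderate); at 3.0, 253.2 (Normal) against 28.1 (Severe).
- 80 years, 60 kg: Moderate under both readings from 0.8 mg/dL (34.0 against 53.1) to 1.2 mg/dL (51.0 against 35.4).

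**Effect on a baseline table.** This uses simulated women with age uniform from 18 to 75, weight of mean 72 kg (SD 14, limited to 40–120 kg) and normally distributed creatinine. All of these inputs are assumptions.

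| Mean Scr (SD) | Normal: bracketed → printed | Moderate: bracketed → printed |
|---|---|---|
| 0.70 (0.12) | 75% → 4% | 3% → 59% |
| 0.75 (0.15) | 68% → 8% | 5% → 51% |
| 0.85 (0.20) | 54% → 18% | 11% → 39% |

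**The case against.** **The SAP names the method.** A programmer who uses Cockcroft and Gault from a standard source gets correct values whatever the line says. The SAP also refers laboratory displays to the sponsor's data standards and the output programming specifications, which are not available here. This stands: the error is conditional on literal coding, and nothing shows that wrong categories will be produced. It does not clear the text, because the SAP prints an explicit equation that disagrees with the method it names, and anyone who codes or checks from the text would carry the error forward.

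**The layout may have been lost in text extraction.** This is a weak defence. The line has an inline slash and balanced brackets, the QTc formulas in 4.5.4.3 kept their fraction bars, and the ALT/ALP ratio in the same section kept a bracketed denominator. A look at the source PDF settles it.

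**A stronger reading is tempting:** that the renal categories come out reversed, with healthy women shown as impaired and impaired women as normal. The documents do not support it.
- Even if coded literally, the result is not a mirror image. The distortion is creatinine squared, and the effects of age and weight are kept. For 40 years and 70 kg both readings give Mild from about 0.93 mg/dL (82.6 / 89.5 = 0.92) to 1.08 mg/dL (89.5 / 82.6 = 1.08).
- Exclusion 13 makes high creatinine uncommon, so the 2.0 mg/dL row above is an edge case. It is not impossible: protocol 1.3 (footnote i) and 8.3.4 allow for exclusionary central laboratory results that arrive during treatment.

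**The reach is small.** This also stands. The CSS outcomes, the clinically evaluable sets and the primary analysis do not use clearance. Exclusion 13 refers to creatinine clearance but does not cite this formula, so no effect on eligibility is shown. The imputation covariates (4.2.3) and the other analyses (4.6) are redacted, so no wider use can be claimed.

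**Conclusion.** The printed formula is wrong as written. For a given age and weight it makes estimated clearance rise with creatinine, against the named method, the SAP's severity scale and protocol exclusion 13. The direction of the error follows from the documents alone.

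The consequence depends on the line being coded as printed. The planned baseline renal impairment category for the ITT and CE24 sets would then be wrong, mainly by labelling many women with normal clearance as Mild or Moderate, while the few with raised creatinine would look too healthy. Under the assumed populations, the share classed as Normal falls by 36 to 71 percentage points (54 − 18 and 75 − 4). Those sizes rest entirely on the assumed distributions of age, weight and creatinine.

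Because the visible use is descriptive and the method is named, this is a minor correction.

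**What to change.** In SAP 4.5.4.1, print the formula as ((140 − age) × weight × 0.85) / (72 × serum creatinine in mg/dL). Check the output programming specification and the derivation code against it; one hand-calculated record with creatinine away from 1.0 mg/dL is enough to tell the two readings apart. The cost is one pair of brackets and a short programming check. No data collection or other analysis changes.

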#### 4.5.4.2. Vital Signs

The analyses of vital signs parameters will be based on GSK Core Data Standards.

The following vital signs measurements will be reported before blood collection for laboratory tests for the study at baseline.

- Temperature
- Systolic and Diastolic blood pressure
- Respiratory rate
- Pulse rate

Descriptive statistics (n, mean, standard deviation (SD), median, minimum value (min), and maximum value (max)) will be presented for quantitative measurements of vital signs parameters at baseline and worst-case post-baseline assessments from unscheduled visits (only if there are at least **10** participants with data at unscheduled visits) Participants listing for vital signs parameters will be presented.

Details of the planned displays for vital signs parameters are provided in Output programming specifications (OPS) and will be based on GSK Data Standards and statistical principles.

#### 4.5.4.3. ECG

The analyses of ECG parameters will be based on GSK Core Data Standards.

The arithmetic mean of the three recorded ECG measurements will be presented in all data summaries and participant listings. ECG measurements at baseline will be recorded, including heart rate, PR interval, QRS duration, QT interval, QRS axis and RR interval. Corrected QT intervals will be calculated in case of not correctly entered in eCRF by Bazett's formula.

$$QTcB \text{ (msec)} = \frac{QT}{\sqrt{RR/1000}}$$

and by Fridericia's formula:

[figure not shown]
$$QTcF \text{ (msec)} = \frac{QT}{\sqrt[3]{RR/1000}}$$

Descriptive statistics (n, mean, standard deviation (SD), median, minimum value (min), and maximum value (max)) will be presented for quantitative measurements of ECG parameters at baseline and worst-case post-baseline assessments from unscheduled visits (only if there are at least **CCI** participants with data at unscheduled visits) Participants listings will be provided for all parameters of ECG values and findings at baseline including abnormal ECGs including unscheduled visits.

Details of the planned displays for ECG parameters are provided in Output programming specifications (OPS) and will be based on GSK Data Standards and statistical principles.

#### **4.6. Other Analyses**

**CCI**

[figure not shown]
## 4.7 Interim Analyses

Not Applicable.

## 4.8 Changes to Protocol Defined Analyses

[figure not shown]
- The CE definitions here included additional clarifications compared to the protocol.

CCI

## 5 SAMPLE SIZE DETERMINATION

CCI

[figure not shown]
## 6 SUPPORTING DOCUMENTATION

### 6.1 Appendix 1 Study Population Analyses

The study population analyses will be based on the Intent to Treat (ITT) Analysis Set, unless otherwise specified. Some selected study population analyses will also be presented by the CE24 set.

Study population analyses will be included analyses of participant's disposition, protocol deviations, demographic and baseline characteristics, prior and concomitant medications, study intervention compliance based on GSK Core Data Standards.

CCI

Details of the planned displays for study population analyses are provided in Output programming specifications (OPS) and will be based on GSK Data Standards and statistical principles.

#### 6.1.1 Participant Disposition

Participant disposition will be tabulated for study treatment (gepotidacin) with the counts and percentages of participants who complete the study, prematurely withdraw, and the reason for study withdrawal for ITT analysis set and primary clinically evaluable at 24 hours ( $\pm 4$  hours) analysis set. Participant listing of the reasons for study withdrawal will be provided.

Summary of treatment status and reasons for discontinuation of study treatment will be produced for study treatment (gepotidacin), with the number of participants who completed treatment, or prematurely discontinued treatment, and the primary reasons for treatment discontinuation tabulated for the ITT analysis set and primary clinically evaluable at 24 hours ( $\pm 4$  hours) analysis set. Participant listing of the reasons for treatment discontinuation will also be provided.

Summary of reasons for screen failure (did not meet inclusion/exclusion criteria, adverse event, protocol deviation, lost to follow-up investigator discretion, participant withdrew consent, or other) will be provided for screened participants. A listing for participants with inclusion/exclusion criteria deviations will be generated.

A summary of the number of subjects by site will be produced using ITT analysis set and primary clinically evaluable at 24 hours ( $\pm 4$  hours) analysis set.

A table will be generated for summarizing the number of participants in each analysis set for all participants who provided informed consent. A listing for exclusion of participants from each analysis set will be produced. A separate table will also be constructed that summarizes the reasons for exclusion from each study analysis set for all participants in the ITT analysis set.

### 6.1.2 Demographic and Baseline Characteristics

Demographic characteristics such as age, sex, race, ethnicity, childbearing potential, baseline renal impairment category, height, weight, and body mass index (BMI), and baseline history of acute cystitis recurrence will be summarized and tabulated for study treatment using participants in ITT and primary clinically evaluable at 24 hours ( $\pm 4$  hours) analysis set.

Descriptive statistics will be presented for age, height, weight, and BMI. Counts and percentages will be presented for age category ( $\leq 50$  and  $> 50$ ), sex, race, ethnicity, childbearing potential.

Individual participant demographics characteristics will be presented in listings.

CCI

A large black rectangular box redacting content.

### 6.1.3 Protocol Deviations

Important protocol deviations will be summarized.

Protocol deviations will be tracked by the study team throughout the conduct of the study in accordance with the Protocol Deviation Management Plan, entitled Study Deviation Tool and Rules. These protocol deviations will be reviewed to identify those considered as important as follows:

Data will be reviewed prior to freezing the database to ensure all important deviations, which may lead to exclusion of a participant from the analysis sets are captured and categorised in the protocol deviations dataset.

This dataset will be the basis for the summaries of important protocol deviations.

A separate participant listing of all inclusion/exclusion criteria deviations will also be provided. This listing will be based on data as recorded on the inclusion/exclusion page of the eCRF.

#### 6.1.4 Prior and Concomitant Medications

Prior and Concomitant medications will be coded using the WHO Drug dictionary at the time of reporting. Counts and percentages will be presented for prior and concomitant medication by Anatomical Therapeutic Chemical (ATC) classification Level 1 (Body System) information and Ingredient using ITT analysis set and primary clinically evaluable at 24 hours ( $\pm 4$  hours) analysis set. A systemic antimicrobial is regarded as an antibiotic used for treating uUTI or other infections.

CCI

The summary of concomitant medications will present separate summaries for systemic concomitant medications, non-systemic concomitant medications, systemic antibiotics taken for the disease under study (either started before treatment start date and continued in the treatment period, or, started on/after treatment start date), systemic antibiotics taken for another disease/condition (either started before treatment start date and continued in the treatment period, or, started on/after treatment start date) and prohibited (non-antibiotic) medications.

An antibiotic is considered systemic if the route is oral, subcutaneous, intramuscular, intravenous, or rectal.

All prior and concomitant medications, as well as prior and concomitant antibiotic medications for uUTI, will be provided in separate listings.

